6.3 Adverse events and unanticipated problems

For provider-subjects, the EHR decision support designed for this trial is only meant to highlight information that could be useful in patient management and prescribing. Therefore, we do not anticipate any safety issues to arise with regards to provider-subjects who receive the electronic decision support, and the IRBs who have reviewed our prior proposals have agreed with this general approach.

For patient-subjects, we do not anticipate the occurrence of any adverse events as a result of providers receiving decision support aimed at reducing the use of potentially unsafe medications that already have established clinical guidelines advising against their use. The decision support provides resources to help patients safely discontinue the high-risk medications under study (e.g., providing tapering guidelines and facilitating the substitution of lower-risk therapies). There is a theoretical risk of precipitating withdrawal, but the risk is less than the continued risks of ongoing use of the drugs being addressed by the interventions (See Section 8.5 for further detail).

We will ensure the safety of patient-subjects by leaving ultimate clinical decision-making in the hands of the evaluating provider who is in charge of caring for the patient. The study team will not be providing any direct care to patients, and all treatment decisions will ultimately be made by the patients' own medical teams. As a result, any adverse events will be handled in the course of regular clinical care. Further, to maximize the generalizability of the results and to avoid co-intervention, patients will not be required to have study-specific monitoring as part of the proposed pragmatic trials. Therefore, we do not plan to use any patient-directed prospective monitoring of Adverse Events (AEs) or Significant Adverse Events (SAEs) in this trial. An *Adverse Event (AE)* is defined as any untoward or unfavorable medical occurrence in a human study participant, including any abnormal sign (e.g. abnormal physical exam or laboratory finding), symptom, or disease, temporally associated with the participants' involvement in the research, whether or not considered related to participation in the research.

- Adverse Events will be classified using the following rating scales:
 - o Severity: Mild, Moderate or Severe
 - Mild: Awareness of signs or symptoms but are easily tolerated
 - Moderate: Events introduce a low level of inconvenience or concern but may interfere with daily activities but are usually improved by simple therapeutic measures
 - Severe: Events interrupt the participants' normal daily activities and generally require systemic drug therapy
 - o Expectedness: Unexpected or Expected
 - Unexpected: nature or severity of the event is not consistent with the condition under study
 - Expected: event is known to be associated with the intervention or condition under study.

Serious Adverse Event (SAE) are defined as any adverse event that results in death, is life threatening, or places the participant at immediate risk of death from the event as it occurred, requires or prolongs hospitalization, causes persistent or significant disability or incapacity, results in congenital anomalies or birth defects, and is another condition which investigators judge to represent significant hazards.

However, our plan for data and safety monitoring does include multiple mechanisms to ensure minimal risk of participation in the trials. We will leverage an automatic adverse event reporting and review system to observe and monitor for any SAEs that do occur. In specific, providers report adverse events through an online reporting system. All reports are routinely reviewed by quality and safety specialists at Atrius. Atrius, under the oversight of our Site PI, will use these reports to monitor for AEs and SAEs throughout the course of the study. Any reports of deaths will be submitted to the NIA Program Officer and to the Data Safety Monitoring Board (DSMB) Chair or designated DSMB member within 24 hours. Any unanticipated SAEs deemed by the specialists and Site PI at Atrius to be related to the intervention will be reported to the NIA PO and to the DSMB Chair or to the designated DSMB member within 48 hours of the study's knowledge of the SAE. All other reported SAEs and AEs received by the study team will be reported to the NIA Program Officer and to the DSMB quarterly, unless otherwise requested by the DSMB or a Safety Officer.

7. Statistical Considerations

7.1 Statistical Hypotheses

Our null hypothesis will be that rates of provider prescribing (defined by evidence of a reduction in prescribing of high-risk medication) in any one of the intervention groups (defined by factors) will be no different than in the other arms, including the usual care arm.

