To determine whether EHR-tools designed using behavioral science principles are more effective than at reducing inappropriate prescribing of high-risk medications in older adults than standard EHR tools or usual care.	Composite of 1) discontinuation of high-risk medications (benzodiazepines, sedative hypnotics, or anticholinergics [in secondary analyses]) or 2) ordering a gradual dose taper for one of these medications	These outcomes are rapidly measurable using EHR data alone and will provide evidence of provider behavior change.
Secondary		
To examine whether behavioral science-based EHR tools reduce cumulative prescribing of high-risk medications in older adults compared with usual care.	Quantity of high-risk medication prescribed, defined by number of milligram equivalents of high-risk medications prescribed to patients in follow-up	These outcomes capture the extent to which high-risk medications are cumulatively prescribed to patients by all Atrius providers over the follow-up period.
Tertiary/Exploratory		
To evaluate whether behavioral science-based EHR tools reduce the risk of clinically-significant adverse drug events, falls, fractures, hospitalizations, or emergency room visits compared with usual care.	Rates of adverse drug events, falls, fractures, hospitalizations, and emergency room visits in follow-up; quantity of high-risk medications dispensed to patients in follow-up period	These outcomes measure clinical outcomes that are consequences of these high-risk medications, measured in medical and pharmacy administrative claims data.

3. Study Design

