7.2 Sample size determination

Adaptive Trial

We powered the study for 15 active intervention arms with the following assumptions. We assumed a baseline rate of the composite outcome of 5% (i.e., that 5% of patients would have a medication discontinued or a taper ordered in the follow-up window), an intervention effect size of 15% (i.e., Odds ratio of 1.15 of discontinuation compared with usual care), alpha=0.05, power=0.8, and patient correlation of 0.3 within randomized providers. We also assumed an average cluster size of 20 patients per provider based on pilot data.

Replication Trial

Using pilot data from MGB analysts, we should have >80% power to detect absolute differences of 10% or smaller in the primary outcome between each of the intervention arms and usual care, assuming an intra-provider correlation of 0.1 and using a Holm-Bonferroni correction. We should also be sufficiently powered to detect meaningful differences in the clinically significant adverse events.

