7.3 Statistical analyses

7.3.1 *Analysis of the primary endpoints*

7.3.1a Adaptive trial

The unit of analysis is at the patient-level. Therefore, for the primary outcome, we will use a generalized linear mixed model for binary outcomes to adjust for physician-level

clustering and multiple patient observations per physician. The study arms will be analyzed using a multivariable regression model, in which each of features of the EHR tools (“factors”) will be included as covariates in an overall regression model that compares the effect of receiving an enhanced EHR decision support tool compared with usual care. In specific, these factors will include: timing of EHR tool (open encounter=1, order entry=0), whether a follow-up alert is enabled as part of the tool (yes=1, no=0), cold state outreach is used (yes=1, no=0), simplification is used (yes=1, no=0), sign-off is used (yes=1, no=0), pre-commitment is used (yes=1, no=0) or if different risks of the high-risk medications are presented within the EHR tool (yes=1, no=0). In this way, we will also observe and report an overall effect of the enhanced EHR tool compared with usual care as well as the effect of individual features through their coefficients in the model. We will conduct this interim analysis once at the end of follow-up in Stage 1 to determine the arms with the most potential promise. In specific, the 15 active arms will be ranked based on their observed effect size at reducing prescribing of high-risk medications from the covariate coefficients from the models. At the end of follow-up in Stage 1, we will also use these regression models to explore whether any of the intervention arms (defined by factors) are inferior to usual care. We will repeat these analyses at the end of Stage 2 using all available data to determine whether any of the intervention factors (and secondarily, arms) were more effective than usual care at reducing prescribing of high-risk medications. In secondary analyses, we will include anticholinergics.

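### The adaptive trial's formal null does not match its objective or its final test, the overall tool effect has no place in the order of tests, and no multiplicity rule covers the seven factors

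*Combined protocol and SAP*

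**What the plan says.** Five places in the combined protocol and SAP bear on what decides the adaptive trial.

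- **Section 2, overall hypothesis.** Tools built on behavioural principles are compared, as a class, with usual care.
- **Section 2, objectives table.** The primary objective is "To determine whether EHR-tools designed using behavioral science principles are more effective than at reducing inappropriate prescribing of high-risk medications", with standard EHR tools or usual care as the comparator.
- **Section 7.1.** The only formal null is that prescribing "in any one of the intervention groups (defined by factors) will be no different than in the other arms, including the usual care arm".
- **Section 7.2, adaptive trial.** "We powered the study for 15 active intervention arms with the following assumptions", among them "alpha=0.05, power=0.8, and patient correlation of 0.3 within randomized providers". No correction is mentioned. Holm-Bonferroni appears only in the replication paragraph.
- **Section 7.3.1a.** One regression carries seven 0/1 factors: timing, follow-up alert, cold-state outreach, simplification, sign-off, pre-commitment and risk framing. The question at the end of Stage 2 is "whether any of the intervention factors (and secondarily, arms) were more effective than usual care". The same section adds that "we will also observe and report an overall effect of the enhanced EHR tool compared with usual care".

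**The concern.** The section 7.1 null has no direction and takes in comparisons among active groups. Rejecting it need not mean that any tool beats usual care, so it can be rejected without answering the objective.

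Section 7.3.1a asks the right kind of question, with a direction and against usual care, but asks it of any of seven factors. The first-ranked level is therefore itself a multiple test, and no rule controls its error. The overall effect, which is the section 2 hypothesis, is reported alongside with no stated standing.

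The contrasts themselves are also loose. With 0/1 coding, a factor coefficient compares tools with and without a feature. It does not compare a feature with usual care, which is what the final question asks.

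At stake is what a positive adaptive trial means. Section 3.2.3 refers to whether that trial shows superiority of any tool over usual care, and no section says which test would show it.

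**Working it through.** **1. The plan's own figure.** Section 7.2 gives power 0.80 at alpha 0.05 with a 5% baseline, odds ratio 1.15, 20 patients per provider and correlation 0.3. If the figure could be reproduced for one contrast, it would show which contrast was meant.

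- Intervention odds: 1.15 × 0.05/0.95 = 0.0605, so the rate is 0.0605/1.0605 = 5.71%.
- Design effect: 1 + 19 × 0.3 = 6.7.
- Providers (section 3.2.1): about 200, half to usual care and half spread equally over 15 arms, so 100/15 = 6.7 per active arm.

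| Contrast (providers) | Power, odds ratio 1.15 | Power, 15% read as absolute (5% v 20%) |
|---|---|---|
| All active v usual care (100 v 100) | 0.057 | about 1.00 |
| Two-arm factor v usual care (13 v 100) | 0.046 | 0.84 |
| One arm v usual care (7 v 100) | 0.043 | 0.69 |

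These are two-sided tests, counting power in the favourable tail. One-sided versions give 0.104, 0.083 and 0.077 for the odds ratio, and about 1.00, 0.89 and 0.76 for the absolute reading. None is within two points of 0.80, so the power statement does not identify the deciding contrast. The shortfall in power is a separate matter, and this point does not depend on it.

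**2. Do the statements match?**

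| Place | Comparison | Direction | Rank or alpha |
|---|---|---|---|
| Section 2 | Tools as a class v usual care (objective adds standard EHR tools) | Better | None |
| 7.1 | Any one group v the other arms, including usual care | None | None |
| 7.2 | 15 active arms (sizing) | Not stated | 0.05 |
| 7.3.1a, final question | Any factor, then arms, v usual care | Better | Factors before arms; no alpha |
| 7.3.1a, overall effect | Enhanced tool v usual care | Not stated | None |

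**3. What the coefficients estimate.** Arm 1 is enhanced, fires at order entry and has no added feature. In a model with an enhanced indicator and the seven factors, the enhanced coefficient is therefore Arm 1 minus usual care. The average over Arms 1 to 14 is the enhanced coefficient, plus half the timing coefficient, plus one seventh of each of the six feature coefficients. In the Stage 1 layout the standard error of the enhanced coefficient is about 2.1 times that of the average. The overall effect thus has two readings that can disagree.

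**4. Error rate with no true effect.** Assumptions: Stage 1 layout, equal cluster sizes, a separate term for the basic alert (Arm 15), normal test statistics, two-sided 0.05 per test.

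- Each feature contrast is the mean of two arms minus the mean of Arms 1 and 2. Sharing that reference gives the six feature contrasts a correlation of about 0.5 with one another. Timing is balanced and uncorrelated with them.
- Six tests at correlation 0.5: chance of at least one significant result 0.207 (simulated).
- Adding timing: 1 − 0.95 × (1 − 0.207) = 0.247. Direct simulation of the layout gives 0.25.
- Adding the overall average, almost uncorrelated with the factors: 1 − 0.95 × (1 − 0.25) = 0.29. Simulation gives 0.29.
- Favourable results only: 0.13 for the seven factors and 0.15 with the overall effect, against 0.025 for a single test.
- Upper check, independence: 1 − 0.95^7 = 0.30 and 1 − 0.95^8 = 0.34.

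**The case against.** The strongest reply is that the plan does set an order, and that the adaptive trial exists to find promising tools. Much of this stands.

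- A reader might infer that the documents offer four competing deciding hypotheses with no order between them. They do not. Section 7.3.1a puts factors first and arms second. Section 7.2 is a sizing statement, not a hypothesis. The factor wording in 7.1 and in 7.3.1a can be read as one family.
- A reader might also take 7.1 literally and count every pairwise comparison among the arms. No section plans those tests; 7.3.1a specifies one regression with factor covariates.
- A reader might treat chance-positive arms at the end of Stage 1 as false efficacy claims. At that point arms are only ranked, and the check for inferiority is described as exploratory.
- Section 3.2.3 takes two arms forward even without superiority, and the replication trial is sized with Holm-Bonferroni. A false positive in the adaptive trial does not decide whether the replication happens.

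The order does not close the gap. The first level is any of seven tests with no correction, nothing bars arm claims when the factors fail, and the overall effect stays outside the order. The exploratory label in 7.3.1a covers only the Stage 1 inferiority check, whereas the Stage 2 analysis is worded as determining effectiveness.

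**Conclusion.** The point holds in this form: the formal null does not answer the objective or the final question, the overall effect is unranked, alpha and power are stated for the second-ranked level, and no rule covers the first-ranked seven factors. Testing each at two-sided 0.05 gives a false-positive chance of about 0.25 for the factors and 0.29 with the overall effect, against the stated 0.05. Counting only favourable results, it is 0.13 and 0.15.

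These figures assume no true effect anywhere, 100 usual-care providers and about 6.7 per active arm, and equal cluster sizes. Re-randomisation and the selection of up to five arms for Stage 2 are not modelled, so the figures illustrate the gap and are not the error rate of the final analysis. The documents do not support saying that the tests are wholly unordered.

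**What to change.** - **7.1.** Replace the adaptive-trial null with one contrast: no difference in the primary outcome between usual care and the equal-weight average of enhanced Arms 1 to 14, tested at two-sided 0.05. State that this is the combination in step 3 of the working, not the enhanced coefficient.
- **7.3.1a.** If that contrast is significant, test the seven factor coefficients with Holm (smallest p-value against 0.05/7 = 0.0071), described as feature present versus absent. Test arms against usual care with Holm only after all factor hypotheses are rejected, and otherwise report them as exploratory. This keeps factors ahead of arms.
- Give the comparison of enhanced tools with the basic alert (Arm 15), which the primary objective includes, a stated secondary place. Label arm-versus-arm comparisons exploratory. Do the same for claims about arms selected after Stage 1 that reuse Stage 1 data.
- **7.2.** State that alpha 0.05 applies to the single deciding contrast.

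If the sponsor prefers factors first, Holm across the seven factors with a stated place for the overall effect also closes the gap.

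The cost is wording only, with no new data. The downside is that single factors or arms cannot be claimed as confirmed when the deciding contrast is null. They can still be ranked and taken into the replication trial, as section 3.2.3 allows.

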7.2 Sample size determination

Adaptive Trial

We powered the study for 15 active intervention arms with the following assumptions. We assumed a baseline rate of the composite outcome of 5% (i.e., that 5% of patients would have a medication discontinued or a taper ordered in the follow-up window), an intervention effect size of 15% (i.e., Odds ratio of 1.15 of discontinuation compared with usual care), alpha=0.05, power=0.8, and patient correlation of 0.3 within randomized providers. We also assumed an average cluster size of 20 patients per provider based on pilot data.

Replication Trial

Using pilot data from MGB analysts, we should have >80% power to detect absolute differences of 10% or smaller in the primary outcome between each of the intervention arms and usual care, assuming an intra-provider correlation of 0.1 and using a Holm-Bonferroni correction. We should also be sufficiently powered to detect meaningful differences in the clinically significant adverse events.

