3.2.1 Stage 1 Design

In Stage 1 of the trial, we will randomize approximately 200 primary care providers at Atrius Health approximately equally to either usual care or active intervention. Of the half of providers randomized to active intervention, we will randomize them equally to one of 15 active intervention arms. Providers randomized to one of the 15 active intervention arms will receive an EHR tool to guide the care of their eligible patients. Providers randomized to usual care will receive no EHR tool, as is current clinical practice. Providers will be eligible for the trial if they prescribed a

benzodiazepine or sedative hypnotic to at least one older adult in the 180 days prior to randomization. We will randomize providers within strata based on their clinic size and baseline rates of high-risk medication prescribing.

Eligible patients of these providers will be who meet the following criteria: 1) older adults (aged 65 years or more) and 2) who have been prescribed at least 90 pills of benzodiazepine or sedative hypnotic in the last 180 days.

After 6 months (dictated by the average number of observed data points, i.e., at least 1 eligible patient for whom the EHR tools fired per physician), an interim analysis of Stage 1 participants will be performed to rank the 15 active intervention arms based on their observed effect size at reducing prescribing of high-risk medications. Up to 5 of the most promising active intervention arms based on their effect size will be tested in Stage 2. If more than 5 are promising, we will choose the top 5. If 1 to 5 arms are promising, we will choose those for testing in Stage 2. If none are promising, we will combine active interventions within the arms based on the most effective factors. After this interim analysis, the Stage 1 providers in the “winning” arms (i.e., the promising arms) will be randomly assigned to continue to receive their original treatment assignments or to usual care to test holdover/persistency effects. Similarly, the Stage 1 providers assigned to treatment arms determined to be statistically inferior will be randomly assigned in equal proportions to one of the winning arms or to usual care.

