3.2.2 Stage 2 Design

In Stage 2, we will randomize the primary care providers at Atrius Health who were assigned to usual care in Stage 1 in equal proportions to up to one of the 5 most promising treatment arms or to continue to receive usual care. We will also randomize any additional providers who prescribed at least one eligible anticholinergic to at least one older adult in the 180 days prior to randomization for secondary analyses. Providers randomized to one of the 5 selected treatment arms will receive an EHR tool to guide their care of eligible patients. As in Stage 1, we will randomize providers based on demographic characteristics, patient case-mix factors, and

baseline rates of high-risk medication prescribing. Patient eligibility will be identical to that used in Stage 1 except patients will also be included if they had been prescribed at least 90 pills of eligible anticholinergics in the last 180 days. Follow-up in Stage 2 will last at least 8 months, until enough data points have accrued.

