3.2.3 Replication Trial Design

[figure not shown]
This replication trial is a cluster-randomized, NIH-defined Phase III pragmatic trial. The study statistician, in partnership with data analysts at MGB, will generate and implement the randomization scheme, with oversight by the Principal Investigators. All the study sites will be at MGH for this trial; we have received approval from leadership at MGH primary care practices and Digital Health eCare teams to conduct this trial. For study evaluation, data regarding patients' medical history, disease control, medication use, and healthcare utilization will be obtained from EHR data or administrative claims data. The administrative claims data used for evaluation in this study will come directly from MGB in HIPAA-limited datasets through their risk-bearing contracts, as applicable.

We plan to randomize primary care providers at MGH to one of the 2 most promising treatment arms identified in the adaptive randomized trial conducted at Atrius Health or usual care. We expect to randomize approximately 200 providers. Providers randomized to one of the 2 selected treatment arms will receive an EHR tool to guide their care of eligible patients. If the adaptive trial does not demonstrate the superiority of any EHR tools over usual care, we will select the two statistically most promising of the arms for this parallel group trial. We will randomize providers based on provider demographic characteristics, patient case-mix factors, and baseline rates of high-risk medication prescribing measured in EHR data.

[figure not shown]
Providers will be eligible if they prescribed a benzodiazepine, sedative hypnotic, or two distinct anticholinergics to at least one older adult in the 180 days prior to randomization. Providers will receive these EHR tools for their patients who meet the following criteria: 1) older adults (aged 65 years or more), and 2) who have been prescribed at least 90 pills of benzodiazepine or sedative hypnotic or have been prescribed at least one active orders of at least 90 pills of two different anticholinergics in the last 180 days. Follow-up will last 12 months. These patients will also be included in the analyses. The type and timing of EHR tool that the providers receive for these patients will vary based on their assigned intervention arm.

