4.3.2 Inclusivity of study subjects

Atrius Health

Physician and patient subjects will be included based on their meeting eligibility criteria as part of routine care, and the study population will be highly inclusive. Further, pilot data indicate that 201 primary care providers at Atrius currently meet eligibility criteria. Based on these same pilot data, the number of patients included in the analyzable population should exceed 2000 patients in Stage 1 and 4000 patients in Stage 2. Importantly, we expect these participants to cover

a broad range of participants by gender and race/ethnicity. Of these, 59.2% are female, 84.6% are White, 6.4% are Black or African American, 1.4% are Hispanic, 3.1% are Asian/Pacific Islander, 0.3% are American Indian/Native American, and 4.2% are other races or unknown. These estimates at Atrius Health are similar to the overall estimates of older adults in the U.S. Medicare population. Further, given the minimal risk nature of the study, participants will not receive incentives, remuneration, or be required to provide informed consent.

Mass General Hospital.

Physician and patient subjects will be included based on their meeting eligibility criteria as part of routine care, and the study population will be highly inclusive. As at Atrius, we expect these participants to cover a broad range of participants by gender and race/ethnicity. Given the minimal risk nature of the study, participants will not receive incentives, remuneration, or be required to provide informed consent.

5. Study Interventions

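### Section 7.2 states 0.8 power for an odds ratio of 1.15, but about 200 providers give about 7–9% for the Stage 1 overall contrast and well under 80% with both stages pooled

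*Combined protocol and SAP*

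**What the plan says.** Section 7.2 (Adaptive Trial) gives a 5% usual-care rate of the composite outcome, an average of 20 patients per provider, and "Odds ratio of 1.15 of discontinuation compared with usual care), alpha=0.05, power=0.8, and patient correlation of 0.3 within randomized providers". It says the study was powered for 15 active arms, and derives no number of providers or patients from these inputs.

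The numbers are elsewhere. Section 3.2.1: "we will randomize approximately 200 primary care providers at Atrius Health approximately equally to either usual care or active intervention", with the active half divided equally among 15 arms. Section 4.3.2: 201 providers currently meet the criteria, and "the number of patients included in the analyzable population should exceed 2000 patients in Stage 1 and 4000 patients in Stage 2".

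Providers are re-randomised for Stage 2. Those from losing arms, "determined to be statistically inferior will be randomly assigned in equal proportions to one of the winning arms or to usual care". Those from winning arms are randomised to stay or move to usual care, in a ratio that is not given. Those on usual care in Stage 1 go "in equal proportions to up to one of the 5 most promising treatment arms or to continue to receive usual care" (section 3.2.2).

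The final analysis is pooled, and asks if factors, and in second place arms, beat usual care. Section 7.3.1a: "We will repeat these analyses at the end of Stage 2 using all available data to determine whether any of the intervention factors".

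**The concern.** On a 5% baseline, an odds ratio of 1.15 is a difference of about 0.7 percentage points. Detecting that takes many thousands of patients even without clustering, whereas this design has about 200 clusters with a stated within-cluster correlation of 0.3. The inputs and the stated power look irreconcilable.

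The sentence is the adaptive trial's only sample-size justification. Arms are ranked after Stage 1 on observed effect size, so selection does not formally depend on it. The end-of-Stage-2 test against usual care does. Section 3.2.3 plans for a null result: "If the adaptive trial does not demonstrate the superiority of any EHR tools over usual care, we will select the two statistically most promising". A reader who trusts the 0.8 would take such a null as evidence against an odds ratio of 1.15, which the design could not support.

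**Working it through.** Tests are two-sided at 0.05 and count both tails unless stated; section 7.2 does not give sidedness.

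**1. Effect.** Odds 0.05/0.95 × 1.15 give p2 = 0.05707. Difference d = 0.00707. V = 0.05 × 0.95 + 0.05707 × 0.94293 = 0.1013.

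**2. The plan's own figure.** Section 7.2 gives no provider number, so the 0.8 can only be turned into a requirement.
- Patients per side before clustering: (1.960 + 0.842)² × 0.1013 / 0.00707² ≈ 15,900.
- Design effect on the proportion scale: 1 + 19 × 0.3 = 6.7.
- Providers per side: 15,900 × 6.7 / 20 ≈ 5,330, against about 100 available. With no clustering, 15,900 / 20 = 795.

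**3. Stage 1 overall contrast, 100 v 100 providers, 2,000 patients per side.**
- *0.3 on the proportion scale.* Effective n = 2,000/6.7 = 298.5 per side. SE = √(0.1013/298.5) = 0.0184; d/SE = 0.384. Power = Φ(0.384 − 1.96) + Φ(−0.384 − 1.96) = 6.7% (one-sided 10.4%).
- *0.3 on the latent logit scale of the mixed model.* Between-provider variance is (0.3/0.7) × π²/3 = 1.41. With a marginal rate of 5% this is a proportion-scale correlation of 0.084. Design effect 1 + 19 × 0.084 = 2.60; effective n = 770; SE = 0.0115; power 9.5% (one-sided 15.2%). It is 8.7% if the odds ratio is conditional on provider.
- *No clustering.* SE = 0.0071; power 16.9%.

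The odds ratio detectable with 80% power in Stage 1 is about 2.4 on the proportion scale and about 1.8 (marginal) on the latent scale.

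**4. Both stages pooled.** I used generalised least squares on provider-by-stage proportions. The variance is p(1 − p)[ρ + (1 − ρ)/m], and the covariance between a provider's two stages is p(1 − p)ρr, where r is the between-stage correlation of provider effects. The split with five arms selected is:
- Stage 1 usual care: 83.3 active, 16.7 usual care.
- Winning arms (33.3 providers): half and half, which is assumed.
- Losing arms (66.7 providers): 55.6 active, 11.1 usual care (one sixth).

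Patients are taken as separate in each stage, with no carry-over.

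| Setting (ρ = 0.3 unless stated) | Power |
|---|---|
| 20 patients per provider per stage, stage effect, r = 1 | 22.0% |
| Same, no stage effect | 24.7% |
| Same as first row, losing arms split half and half | 27.5% |
| Same as first row, 10 then 20 patients | about 16% |
| Same as first row, r = 0.8 | 11.6% |
| Same as first row, r = 0.5 | 8.9% |
| Same as first row, r = 0 | 7.9% |
| Same as first row, ρ = 0.084 | 19.5% |

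The range is roughly 8–28%.

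**5. A best case for pooling.** Suppose every provider had half of its patients on each side, with a fully stable provider effect. The variance is then (1 − 0.3) × 0.1013 / (T/2).
- T = 6,000 (2,000 + 4,000, the minima in section 4.3.2): SE = 0.00486; power 31%.
- T = 8,000 (200 × 20 × 2): SE = 0.00421; power 39%.
- One-sided: 42% and 51%.
- 80% two-sided would need 2 × 15,900 × 0.7 ≈ 22,260 patients.

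**6. If 15 percentage points was meant (5% to 20%), Stage 1, design effect 6.7.** V for 100 v 100 is 0.0475 + 0.16 = 0.2075.
- Overall, 100 v 100: SE = √(0.2075/298.5) = 0.0264; power above 99%.
- Single arm, 7 v 100: SE = √(0.0475/298.5 + 0.16/20.9) = 0.0884; power about 40%.
- Two-arm factor, 13 v 100: SE = √(0.0475/298.5 + 0.16/38.8) = 0.0654; power about 63%.

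The single-arm and factor figures are approximate because clusters are few.

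**The case against.** The strongest reply is that section 7.2 lists inputs and names no contrast, so the certain defect is an incomplete statement, and that the adaptive design recovers information because re-randomised providers serve as their own controls. The second part is true: pooling can raise power from about 7% to the twenties. It does not approach 80% in any setting tried. The first part does not rescue the figure either, because saying that the study was powered at 0.8 is a claim about this design.

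Several cautions stand:

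- A reader might infer a sharp pooled figure, such as 20–23%, or a definite share of trials that would miss the effect. The documents do not support that precision. They leave open the winning-arm ratio and how losing arms divide. They name no stage term, and say nothing on the stability of provider effects or patient overlap between stages. Section 3.2.1 itself expects that holdover may occur.
- A reader might infer that 31–39% is an absolute ceiling. It is conditional on 6,000–8,000 patients. Section 4.3.2 gives minima, section 3.2.2 lets Stage 2 run until enough data accrue, and it is not said whether the 4,000 includes anticholinergic patients, who are reserved for secondary analyses.
- The planned overall contrast is the enhanced tool against usual care, and arm 15 is a basic alert. About 93 active providers, not 100, are then enhanced (100 × 14/15). Power becomes 6.6% and 9.3%, an immaterial change.
- A reader might conclude that the effect was simply mislabelled. The text defines the 15% as an odds ratio, so this is speculation; it would also leave single-arm and factor contrasts below 0.8 in Stage 1.

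**Conclusion.** The concern holds. The stated 0.8 power at an odds ratio of 1.15 is not delivered by about 200 providers with 20 patients each. The Stage 1 overall contrast has about 7% (proportion scale) or about 9% (latent scale), and about 17% even if clustering is ignored. These rest only on figures in the documents, plus a two-sided test and the two readings of the correlation. The pooled 8–28% rests on the listed assumptions and should be read as a range. Factor and single-arm contrasts draw on fewer providers.

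This does not show that the design or the analysis model is invalid, or that Stage 1 selection fails. The error is in the stated justification, and it matters most for reading a null result at the end of Stage 2.

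**What to change.** In section 7.2, delete or correct the claim of 0.8 power for an odds ratio of 1.15. State:

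- the powered contrast (overall enhanced tool v usual care, factor, or arm) and the analysis stage (Stage 1 or pooled);
- the number of providers and patients;
- sidedness, effect scale, and whether 0.3 is on the proportion or the latent logit scale.

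Then restate the power, or the detectable effect, for that contrast. Any pooled figure should give the number of arms selected, the re-randomisation split, and the assumptions on stage effect, provider stability, carry-over and patient overlap. Factor or arm figures should come from a method suited to few clusters. The numbers above are checks, not replacement text.

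If 15 percentage points was intended, replace the odds ratio with 5% to 20% and show the power for the named contrast.

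Cost: protocol and SAP wording and one recalculation. Enrolment, design and analysis do not change. The downside is that the stated figure becomes less favourable, unless the effect scale was mislabelled and the overall contrast was meant.
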